The BKFO test is performed in either general anesthesia or spinal anesthesia, for patients operated in Bordeaux and Paris, respectively. This is standard procedure for the surgical procedures and also prevents any voluntary activation of the adductor muscles. The patient lies supine on the surgical table with approx. 90° knee flexion, 45° hip flexion, and the feet together and the hips in external rotation (also known as the frog-leg position). Standardization of position is achieved by flexing one leg first, so the medial malleolus is placed next to the medial knee joint line of the contralateral leg. The knee is then moved laterally, externally rotating the hip with the plantar surface placed towards the contralateral leg. The contralateral leg is then flexed, and the plantar surfaces of the feet are aligned. The distance between the most distal point on the head of the fibula and the surface of the surgical table is measured using a rigid tape measure and distance is recorded in cm to the nearest 0.5 cm (Figure 1) The BKFO test has excellent reproducibility with a standard error of the measurement of approx 1 cm or less.[4,11,12]

[figure not shown]

Figure 1 A: Position of the patient's legs prior to the surgical procedure, B: Measurement from the head of the fibula to the surgical table

Surgical procedure

The proximal adductor longus tendon is identified through palpation, and a longitudinal incision of approximately 4cm is made in the line of the tendon. The fascia of the adductor longus is divided to identify the tendon (figure 2), and a transverse incision is made as close to the insertion as possible (approximately 0.5cm) resulting in a full release of both the adductor longus tendon and muscle, as present on the posterior side of the tendon. A minor removal of approximately 0.5 cm of the released tendon is made, and the adductor longus is placed approximately 5 cm from the pubic bone (figure 2). The wound is closed in layers after careful hemostasis. The tenotomy is either performed unilateral or bilateral.

[figure not shown]

Figure 2 Adductor longus tendon before and after the tenotomy.

Statistical analysis

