Data are presented as means with standard deviation (SD), unless indicated otherwise, and non-normally distributed data are expressed as medians with the 25th–75th interquartile range (IQR₂₅, IQR₇₅). A paired T-test is used to compare the BKFO results pre- and post- tenotomy. Additionally, correlation between baseline values and change in BKFO will be analyzed to investigate whether patients with higher baseline test results also have a larger change. Analyses are carried out in Statistical Package for Social Sciences (SPSS; version 21, IBM). Effect sizes were calculated using Cohen's d and assessed as; small ($d = 0.2$), moderate ($d = 0.5$), and large ($d = 0.8$).[13]

Sample size

We calculated our sample size using G*power software (v. 3.1, Heinrich-Heine-Universität, Düsseldorf, Germany). We used BKFO values from non-injured football players; mean 13.1 cm, standard deviation (SD) 4.4cm.[4] We performed pilot measurements pre- and post-tenotomy on five patients. These had a

mean of 2.1 cm reduction, which we used for the sample size calculation. We set the required power at 95%, used an α -error probability of 5%, and a correlation between measurements of 0.5. This resulted in a total sample size requirement of 60 participants.

REFERENCES

- 3 Hölmich P. Long-standing groin pain in sportspeople falls into three primary patterns, a “clinical entity” approach: a prospective study of 207 patients. *Br J Sports Med* 2007;**41**:247–52. doi:10.1136/bjism.2006.033373

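### Does the assumed pre-post correlation of 0.5 clash with the stated measurement error of about 1 cm, and so undermine the sample size of 60?

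*Combined protocol and SAP*

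**What the plan says.** The Statistical analysis section fixes the primary test: "A paired T-test is used to compare the BKFO results pre- and post- tenotomy". The Sample size section then gives the inputs. For spread: "We used BKFO values from non-injured football players; mean 13.1 cm, standard deviation (SD) 4.4cm". For the effect: "We performed pilot measurements pre- and post-tenotomy on five patients", which gave a "mean of 2.1 cm reduction, which we used for the sample size calculation". Power is set at 95% and the type I error at 5%, with sidedness not stated. The last input and the result are "and a correlation between measurements of 0.5. This resulted in a total sample size requirement of 60 participants". No source is given for the 0.5, and the SD of the five pilot changes is not reported.

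The BKFO section credits the test with "a standard error of the measurement of approx 1 cm or less" and has distances recorded to the nearest 0.5 cm. The sample-size calculation does not use the measurement error. The plan sets no threshold in cm for the mean change; its size is to be described by means with SD and by Cohen's d.

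**The concern.** In a paired design, power depends on the SD of the within-patient change. The plan does not estimate that SD directly. It builds it from a between-person SD in a different population and an unsourced correlation. With a measurement error of 1 cm, two readings on an unchanged patient would differ with an SD of only about 1.4 cm, whereas the plan works with 4.4 cm.

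If the smaller figure were nearer the truth, 95% power would be a poor description of a study of 60. Power for 2.1 cm would be close to 100%, a significant result would be almost automatic at the planned effect, and a mean change well under 1 cm could reach p < 0.05. The Introduction asks whether and by how much the muscle affects the test, and a p-value against zero says little about the second part. The pilot pairs, which bear directly on the SD of change, supplied only their mean.

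**Working it through.** **Inputs.** SD of one measurement 4.4 cm, mean change 2.1 cm, correlation r = 0.5, power 95%, alpha 5% (Sample size); paired t-test (Statistical analysis); measurement error (SEM) 1 cm, the upper end of the stated range (BKFO section).

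**Step 1: the plan's own figure.**
- SD of change = 4.4 × √(2 × (1 − 0.5)) = 4.4 cm.
- Standardised effect = 2.1 / 4.4 = 0.477.
- Exact noncentral t, two-sided 5%: power is 94.998% at n = 59 and 95.3% at n = 60. The stated 60 reproduces. A one-sided test would need 49, so the calculation was two-sided.

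**Step 2: what r = 0.5 implies beside an SEM of 1 cm.**
- Measurement error alone gives an SD of change of √2 × 1 = 1.41 cm, and a repeat-reading correlation of 1 − 1²/4.4² = 0.948.
- To reach 4.4 cm, true effects must vary between patients with SD √(4.4² − 2) = √17.36 = 4.17 cm around a mean of 2.1 cm. Under normality, about 31% of patients would then truly move in the wrong direction.
- With no variation in effect, r = 0.5 would need an SEM of 4.4 × √0.5 = 3.1 cm.

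So 0.5 is possible but looks low.

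**Step 3: what follows if r is higher.** The documents do not give the true value, so a range is shown. The last column is t(0.975; 59 df) × SD of change / √60, which is also the half-width of the 95% confidence interval.

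| r | SD of change (cm) | N for 95% power | Power at 60 | Smallest significant mean change (cm) |
|---|---|---|---|---|
| 0.5 | 4.40 | 60 | 95.3% | 1.14 |
| 0.6 | 3.94 | 48 | 98.2% | 1.02 |
| 0.7 | 3.41 | 37 | 99.7% | 0.88 |
| 0.8 | 2.78 | 25 | >99.9% | 0.72 |
| 0.9 | 1.97 | 14 | >99.9% | 0.51 |
| 0.948 | 1.41 | 9 | >99.9% | 0.37 |

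The last row assumes that every patient has the same effect, which the documents do not say. On the plan's own inputs the smallest significant mean change is 1.14 cm, above the SEM. It falls below 1 cm only when the SD of change is under 3.87 cm, that is r above about 0.61.

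**Step 4: is 1 cm the right yardstick for a mean?** The SEM describes a single reading. Over 60 patients, random measurement error adds 1.41 / √60 = 0.18 cm to the standard error of the mean change. A mean change below 1 cm can therefore be real and well estimated, and finding it significant is not a false positive.

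**Step 5: could the pilot SD have served instead?** With five pairs (4 degrees of freedom), the 95% confidence interval for an SD runs from about 0.6 to 2.9 times the estimate. That is too wide to fix a sample size on.

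**The case for a change.** The strongest case for acting does not need a uniform effect. Suppose true effects vary with an SD of 2.1 cm, as large as their mean. Then the SD of change is √(2 + 2.1²) = 2.53 cm, r is about 0.83, 21 patients give 95% power, and 60 give more than 99.99%. Even this generous variation does not approach 0.5. The pilot pairs come from the right patients and procedure, their SD goes unreported, and a few sentences would put the paragraph in order and tie the conclusion to the mean change in cm with its confidence interval.

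Part of this stands. The 0.5 is unsupported and probably conservative, and a sentence saying so, with the pilot SD, would have been good reporting. But the SEM comes from reproducibility work, while a correlation across an operation also takes in differences in surgical effect and re-positioning of the legs. The Surgical procedure section allows unilateral or bilateral release in a test that flexes both legs, so some variation in effect is to be expected. A corrected power figure could not be stated anyway, because the pilot SD is not in the documents.

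On the question of how much, the plan already reports means with SD and an effect size. A confidence interval for the mean change follows from the mean, SD and number of the changes, and is routine with a paired t-test. A larger sample sharpens that answer. Reading the group mean against a 1 cm single-reading error would add a confusion, not remove one.

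**Conclusion.** No change is needed. The sample-size arithmetic is correct (60 participants, 95.3% power), and the stated measurement error does not contradict r = 0.5. The correlation is unsourced and probably too low, but that errs on the safe side: at any correlation of 0.5 or more, power for 2.1 cm is at least 95% and the expected half-width of the 95% confidence interval is at most about 1.14 cm. The planning value plays no part in the analysis, since the paired t-test uses the observed SD of the changes. Enrolling more than the minimum costs these patients little, because they are having the tenotomy anyway and the study adds only measurements.

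This rests on the plan's 4.4 cm SD and 2.1 cm effect and on equal variances before and after surgery; the 31% figure also assumes normality. What remains is missing detail (a reason for 0.5, the pilot SD, an explicit confidence interval) that analysts can supply when reporting without altering the design or the test.
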